### 11.2 Serious Adverse Event (SAE)

SAE is any adverse event occurring following study mandated procedures, having received the IMP or placebo that results in any of the following outcomes:

1. Death
2. A life-threatening adverse event
3. Inpatient hospitalisation or prolongation of existing hospitalisation
4. A disability / incapacity
5. A congenital anomaly in the offspring of a participant

Important medical events that may not result in death, be life-threatening, or require hospitalisation may be considered a serious adverse event when, based upon appropriate medical judgment, they may jeopardize the patient or participant and may require medical or surgical intervention to prevent one of the outcomes listed in this definition

A distinction is drawn between serious and severe AEs. Severity is a measure of intensity whereas seriousness is defined using the criteria above. Hence, a severe AE need not necessarily be serious.

All reportable SAEs, must be assessed for causality by the PI or delegate.

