3. Assess the safety of using potent and superpotent TCSs in the vulval area over 24 months	Adverse events	For the duration of participation	Participant reported/clinical assessment/medical notes
4. Assess the cost-effectiveness of the two treatment strategies.	Resource use	At 3, 6, 12, 18 and 24 months	Questionnaire Participant reported
5. Understand the acceptability of reactive and proactive long-term treatment strategies and the barriers and facilitators to continuing with prescribed treatment	Adherence to treatment	At 3, 6, 12, 18 and 24 months	Questionnaire Participant reported
	Acceptability of treatment	At 12 24 months	Questionnaire Participant reported
	Barriers and facilitators	At 12 months	Qualitative interviews

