### Safety

- Development of vulval intraepithelial neoplasia or vulval squamous cell carcinoma at 24 months.
- Targeted adverse events e.g. stinging, skin thinning measured by patient reported symptoms and clinical examination from randomisation over 24 months.

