## 8 TRIAL TREATMENT AND REGIMEN

Trial participants will be allocated to either 'Proactive' or 'Reactive' treatment arm. In the 'Proactive' arm, participants will be prescribed their TCS by their treating physician twice a week for 24 months, regardless of presence of LS symptoms. In the 'Reactive' arm, participants will be allocated to use their TCS only when LS symptoms (or increase in visual signs) are present (please refer to table below for more details). The choice of TCS will be at the discretion of the treating physician. Repeat prescriptions will be obtained by participants as per the usual care.

*Table 6. Intervention vs comparator group*

Treatment group	Proactive Intervention group	Reactive Comparator group
Treatment name	Superpotent or potent topical corticosteroid	Superpotent or potent topical corticosteroid
Formulation	Cream/ointment	Cream/ointment
Dosage	1 application twice-weekly on two non-consecutive days in the absence of symptoms. If symptoms flare, apply once a day until symptoms resolve.	Only use during flare. Apply once a day until symptoms resolve.
Route of administration	Topical (application of a thin layer on affected area)	Topical (application of a thin layer on affected area)
Sourcing	Provided directly as per usual care	Provided directly as per usual care
Packaging and labelling	Topical steroid will be provided and labelled as per usual care prescription, and as required for each patient	Topical steroid will be provided and labelled as per usual care prescription, and as required for each patient

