## 11 ADVERSE EVENTS

An adverse event is any unfavourable and unintended sign, symptom, syndrome or illness that develops or worsens during the period of observation in the study.

An AE includes:

1. Exacerbation of a pre-existing illness.
2. Increase in frequency or intensity of a pre-existing episodic event or condition.
3. Condition detected or diagnosed after medicinal product administration even though it may have been present prior to the start of the trial.
4. Continuous persistent disease or symptoms present at baseline that worsen following the start of the trial.

The interventions being evaluated in this trial are treatments that are widely available within the NHS and used in standard care for lichen sclerosus. Given the well-known safety profile of the interventions, we will adopt a targeted approach to AE reporting.

Reporting and follow-up of these targeted participant and investigator-reported complications associated with the intervention delivery will be recorded in trial e-CRFs in a structured format and do not need to be reported to the Research Ethics Committee (REC).

An AE does not include:

1. Medical or surgical procedure (e.g., surgery, endoscopy, tooth extraction, transfusion); but the condition that leads to the procedure is an AE.
2. Pre-existing disease or conditions present or detected at the start of the trial that did not worsen.
3. Situations where an untoward medical occurrence has not occurred (e.g. hospitalisations for cosmetic elective surgery, social and / or convenience admissions).
4. Disease or disorder being studied or sign or symptom associated with the disease or disorder unless more severe than expected for the participant's condition.
5. Overdose of concurrent medication without any signs or symptoms.

Although all AEs should be recorded in the medical notes, in accordance with GCP, only those AEs which are directly referred to in the e-CRF will be collected for this trial. However, where any AE event meets the criteria of an SAE (see section 11.2), it will require reporting on a SAE form by the PI or delegate.

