#### **11.5 Reporting of Serious Adverse Events**

Participants will be asked to contact the study site immediately in the event of any serious adverse event. Research sites will be asked to contact NCTU immediately (within 24 hours) upon becoming aware of any serious adverse event as described in section 11.2.

Following identification of an SAE, sites will email completed (or partially completed) SAE Form to central coordinating team at the NCTU within 24 hours of becoming aware of the SAE. The investigator (or delegate) must complete, date and sign an SAE form.

Sites will report an SAE by emailing the central coordinating team at the NCTU using a specific SAE mailbox, [[contact]](mailto:[contact]). On receipt of the SAE, the central coordinating team will allocate the SAE a unique reference number, which will then be forwarded to the site as a proof of receipt within 1 working day. If confirmation is not received within 1 working day, the site should contact the NCTU office. The SAE reference number will be quoted on all correspondence and follow up reports regarding the SAE and filed with the actual SAE in the Site File and Trial Master File (TMF).

When an SAE form is completed someone other than Investigator, the Investigator will countersign the original SAE form to confirm agreement with the causality and seriousness assessments. The form should then be returned to NCTU and a copy kept in the Investigator Site File (ISF). The investigator should also report SAEs to their own Trust according to the local practice.

At the NCTU, SAEs on receipt will be reviewed independently by the Chief Investigator, who will be responsible to confirm the seriousness and causality assessment. If the causal relationship is either possibly, probably or definitely related with the trial IMP, this will be regarded as Serious Adverse Reaction (SAR). This SAR will be assessed by the CI for expectedness. If the SAR is unexpected (not defined in the RSI, see section 4.8 of the reference SmPC), it will be classified as a Suspected Unexpected Serious Adverse Reaction (SUSAR).

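### Section 11.2 ties SAEs to receipt of the IMP and no SAE start point common to both arms is given, so by-arm SAE counts could be tilted against proactive treatment

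*Protocol*

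**What the plan says.** **SAE definition.** Protocol section 11.2: "SAE is any adverse event occurring following study mandated procedures, having received the IMP or placebo", followed by the list of serious outcomes.

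**Reporting duty.** Section 11.5 requires sites to contact the trials unit "upon becoming aware of any serious adverse event as described in section 11.2". Section 11 likewise asks for an SAE form when an adverse event meets the 11.2 criteria. It adds that, otherwise, only adverse events named on the e-CRF are collected.

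**Adverse event window.** Section 11 defines an adverse event as one that "develops or worsens during the period of observation in the study". Table 2 in section 3.3 gives the time point for adverse events as "For the duration of participation". Neither depends on receipt of the IMP.

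**First use of the steroid.** Inclusion criterion 2 (section 7.4.1) admits only participants who are asymptomatic at baseline. Table 6 (section 8) sets the proactive regimen as "1 application twice-weekly on two non-consecutive days in the absence of symptoms", and restricts reactive use to flares.

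**Use of the data.** Safety is summarised by counts and percentages per group (section 10.6), and the DMC receives safety reports by arm (section 10.3).

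**The concern.** In a trial where both arms start dosing together, a condition on having received the drug does little harm, because it delays counting equally. Here the time of first application is part of what is randomised. If *received* means applied, the same hospitalisation in the second month would be an SAE in a proactive participant and only an adverse event in a reactive participant who has not yet flared. If it also fell outside the events named on the e-CRF, it would not be collected and could not be recovered at analysis.

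The effect would run one way: fewer countable events in the reactive arm, and so an unfavourable look for proactive treatment in tables that carry no person-time correction. Safety over 24 months is a stated objective (section 3.3), and major safety concerns are a ground for stopping the trial (section 8.9).

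This is separate from the rule in section 10.8 that limits the safety population to participants with at least one dose. That rule decides who is analysed; section 11.2 decides which events exist as SAEs. Correcting 10.8 alone would leave the counts unequal.

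**Working it through.** **Inputs** (section 10.1): reactive rate 4 flares per year, proactive rate 3, dispersion k = 0.34, 90% power, two-sided 0.05, 320 for analysis, 400 randomised (about 200 per arm).

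**1. The plan's own figure.** For two negative binomial rates over one year, with the variance taken under the alternative:

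n per arm = (1.960 + 1.282)² × (1/4 + 1/3 + 2 × 0.34) / ln(0.75)² = 160.4, or 322 in total.

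With the null part of the variance at the pooled rate of 3.5, n = 159.5 per arm, or 320 in total. Then 320 / (1 − 0.20) = 400. The stated sample size reproduces, so the rate and dispersion are being used as the protocol uses them. Nothing in this point challenges it.

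**2. Time to first flare in the reactive arm.** A negative binomial count corresponds to a gamma-distributed individual rate, so with mean rate m per year:

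S(t) = P(no flare by t) = (1 + k·m·t)^(−1/k) = (1 + 1.36t)^(−2.941).

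- Median: (2^0.34 − 1) / 1.36 = 0.195 years, about 2.3 months.
- S(0.25) = 0.42, S(0.5) = 0.22, S(1) = 0.080 (about 16 of 200), S(2) = 0.021 (about 4 of 200).

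**3. Share of the 24-month window before the first flare.**

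∫₀² S(t) dt = [1 − 3.72^(−1.941)] / (1.36 × 1.941) = 0.349 years, or 4.2 months.

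0.349 / 2 = 17.5%. In the proactive arm the corresponding gap is a few days and is taken as zero.

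**4. Apparent ratio under equal true risk.** With a constant SAE hazard unrelated to flares, the proactive:reactive ratio of counted events is 1 / (1 − 0.175) = 1.21.

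**5. Sensitivity.**

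| Reactive rate per year | k | Share lost | Apparent ratio |
|---|---|---|---|
| 4 (protocol) | 0.34 (protocol) | 17% | 1.21 |
| 4 (protocol) | 0.24 | 16% | 1.19 |
| 3 (assumed) | 0.34 | 22% | 1.29 |
| 2 (assumed) | 0.34 | 31% | 1.44 |

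The value 0.24 is what the survey mean of 4.0 and SD of 2.8 imply: (2.8² − 4.0) / 4.0². The protocol does not assume 3 or 2 flares per year for the reactive arm; those rows only show the direction if flares are rarer.

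**6. What the calculation takes for granted.** Receipt means first application, first application coincides with the first flare, every site applies the definition to the letter, the SAE hazard is constant, and the flare rate holds over both years. Steps 3 and 4 are therefore an upper bound at the protocol's rate and dispersion, not a forecast.

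**The case against.** **Receipt may mean supply.** The protocol separates provision from use. Table 6 describes the same sourcing in both arms, section 8.4 has participants given prescriptions without distinction by arm, and section 1.5 speaks of both groups receiving topical steroids. Where a dose is meant, section 10.8 says so. Read this way, the difference between arms largely disappears. This stands as a possible reading, but the protocol does not adopt it, and with no trial dispensing or accountability records (section 8.4) little in the trial would date receipt.

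**Sites may report everything.** Section 11.2 describes seriousness through its listed outcomes, participants are asked to report any serious event, and section 11.5 says all SAEs are recorded. Nothing tells a site to hold back an event because the participant has not flared. This also stands. A reader might infer that a death or hospitalisation before the first flare is definitely not an SAE in this trial; that is the most literal construction, not an established rule.

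**The randomisation wording covers something else.** A reader might set 11.2 against the section 4.4 safety outcome "Targeted adverse events e.g. stinging, skin thinning measured by patient reported symptoms and clinical examination from randomisation over 24 months". That line concerns targeted adverse events, which are reported on the e-CRF under section 11.4 and are not subject to 11.2. The mismatch for SAEs is with the section 11 definition and Table 2 only.

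**The consequence is limited.** No SAE rate ratio is planned, the SAE rate is not a named endpoint, and the protocol gives no expected SAE rate. If, purely for illustration, each arm had 10 true SAEs, the reactive arm would lose 10 × 0.175, fewer than 2. Events before any trial application could not have been caused by it, so SAR and SUSAR detection is unaffected. The documents therefore do not support saying that the DMC would see a false excess; they support saying that it could.

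**Conclusion.** The point holds as an ambiguity with unequal effect. Section 11.2 attaches the SAE definition to receipt of the IMP, two passages make that definition govern reporting, the adverse event window carries no such condition, and no SAE start point common to the arms is given. On one permissible reading, serious events before the first flare could go uncounted in the reactive arm alone.

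The size on the protocol's inputs is at most about 17% of the reactive arm's 24-month window, with an apparent ratio of up to about 1.21 when true risks are equal. It is small if *received* means prescribed or supplied, or if sites report every serious event regardless. The likely origin is template text: the sentence names a placebo, and section 2.5 states that none is used. The correction is worth making because the direction of any distortion is known and the edit is nearly free.

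**What to change.** In section 11.2, replace the condition on having received the IMP or placebo with an explicit window: an SAE is any adverse event meeting a seriousness criterion from randomisation to the end of the participant's follow-up, in both arms, whether or not any topical steroid has been applied. Keep relatedness to the IMP for the SAR and SUSAR step, where sections 11.3 and 11.5 already place it. This brings SAEs into line with section 11 and Table 2, and also removes the reference to a placebo.

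The cost is one sentence in the protocol, matching guidance on the SAE form, and a few more unrelated SAE forms from reactive participants who have not yet flared. No treatment, assessment or sample size changes.

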### 11.3 Causality

**Not related or improbable:** a clinical event including laboratory test abnormality with temporal relationship to trial treatment administration which makes a causal relationship incompatible or for which other drugs, chemicals or disease provide a plausible explanation. This will be counted as "unrelated" for notification purposes.

**Possible:** a clinical event, including laboratory test abnormality, with temporal relationship to trial treatment administration which makes a causal relationship a reasonable possibility, but which could also be explained by other drugs, chemicals or concurrent disease. This will be counted as "related" for notification purposes.

**Probable:** a clinical event, including laboratory test abnormality, with temporal relationship to trial treatment administration which makes a causal relationship a reasonable possibility, and is unlikely to be due to other drugs, chemicals or concurrent disease. This will be counted as "related" for notification purposes.

**Definite:** a clinical event, including laboratory test abnormality, with temporal relationship to trial treatment administration which makes a causal relationship a reasonable possibility, and which can definitely not be attributed to other causes. This will be counted as "related" for notification purposes.

An AE whose causal relationship to the trial IMP is assessed by the PI or Medical Monitor as “possible”, “probable”, or “definite” is an Adverse Drug Reaction.

With regard to the criteria above, medical and scientific judgment shall be used in deciding whether prompt reporting is appropriate in that situation.

#### **11.4 Reporting of adverse events**

Targeted adverse events will be recorded and closely monitored until resolution, stabilisation, or until it has been shown that the trial medication or treatment is not the cause.

In the PEARLS trial these targeted AEs are:

- Progression of scarring
- Pre-cancerous changes to the anatomy
- Infection (thrush and superficial bacterial infection)
- Hypersensitivity, generalised rash
- Cushing’s syndrome
- Local skin burning/skin pain and pruritus
- Allergic/contact dermatitis, erythema, rash, urticaria, local atrophic changes in the skin such as thinning, skin wrinkling, skin dryness, striae and dilatation of the superficial blood vessels (telangiectasias) may be caused by prolonged and intensive treatment with highly active corticosteroid preparations, particularly when occlusive dressings are used or when skin folds are involved.

Sites should report these events via e-CRFs.

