Randomisation and blinding	
Eligible patients who consent will be individually allocated in a 1:1 ratio to either proactive or reactive use of TCS. Treatment will be assigned randomly using a minimisation algorithm with a random element, balancing across groups on:
 
 
• recruitment site
 
• age at randomisation 
 
- children – 5 to <12 years
 
- adolescent – 12 to <16 years
 
- adult – 16 to <45 years
 
- perimenopausal - 45 years & above
 
 
 
• time since last flare (<math>\leq 6</math> months, <math>> 6</math> months)
 
• strength of TCS prescribed (potent or superpotent)
 
 
Allocation will be concealed using a web-based algorithm and held on a secure server, accessed via a secure website.
 
It is not possible to blind the participants, but independent examining clinicians will make assessments of disease activity and scarring at 12 and 24 months and will be blinded to treatment allocation.

Outcome measures	
PRIMARY OUTCOME: Number of flares over 12 months. Flare is defined as worsening of symptoms requiring increased application of TCSs.
 
SECONDARY OUTCOMES: Clinical effectiveness
 
 
• Progression of scarring assessed by blinded assessor at 12 and 24 months by comparing post randomisation assessment to baseline photographs (if patients consented), or assessed clinically if consent has not been given for photographs: 
 
- Adults: scarring worsened (yes/no).
 
- Children and adolescents: failure of normal vulval development (clinical assessment) and/or evidence of scarring (yes/no)
 
 
 

 Symptoms of LS in women and girls include (but are not limited to) itching, burning, pain, painful sexual intercourse, pain on defecation.

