### 4.3 Primary endpoint

Number of flares over 12 months. Flare is defined as worsening of symptoms requiring increased application of TCSs as reported by participants via two weekly reminders.

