### Clinical effectiveness

- Progression of scarring assessed by blinded assessor at 12 and 24 months by comparing post randomisation to baseline photographs (if participant consented), or assessed clinically if consent has not been given for photographs:
  - Adults: scarring worsened (yes/no)
  - Children and adolescents: failure of normal vulval development (clinical assessment) and/or evidence of scarring (yes/no).
- Vulvar Architectural Severity Scale at 12 and 24 months post randomisation (VASS) [30].
- Time to first flare.
- Global clinical severity assessment of LS (5-point ordinal scale) at 3, 6, 12, 18 & 24 months, plus assessed by blinded assessor at 12 and 24 months.
- Condition specific QoL at 3, 6, 12, 18 & 24 months using:
  - Vulvar Quality Life Index (VQLI) (adults) [31]
  - Children's Dermatology Life Quality Index (CDLQI) (adolescents and children) [32].
- Sexual function (adults only) using Female Sexual Function Index [33] at 12 & 24 Months.

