### 10.6 Assessment of safety

Analysis of safety data will be presented descriptively using frequency counts and percentages in each allocated group.

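### Sections 11 and 11.4 conflict on whether LS flare symptoms and scarring progression are adverse events, so the burning/pain/pruritus row and any pooled AE total can mix flares with drug reactions

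*Protocol*

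**What the plan says.** Section 11.4 names the targeted AEs that sites are to report on the e-CRF. Two of them are "Progression of scarring" and "Local skin burning/skin pain and pruritus". Neither carries a condition on attribution, timing or severity.

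The same concepts appear elsewhere as efficacy:

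- The footnote to the primary outcome in the Synopsis reads "Symptoms of LS in women and girls include (but are not limited to) itching, burning, pain", and section 4.3 states: "Flare is defined as worsening of symptoms requiring increased application of TCSs as reported by participants via two weekly reminders".
- Section 4.4 lists, under clinical effectiveness, "Progression of scarring assessed by blinded assessor at 12 and 24 months".

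Among the things an AE does not include, section 11 lists "Disease or disorder being studied or sign or symptom associated with the disease or disorder unless more severe than expected for the participant's condition". The same section counts as AEs the worsening of an existing illness and a rise in the frequency or intensity of an episodic condition.

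On analysis, section 10.6 says: "Analysis of safety data will be presented descriptively using frequency counts and percentages in each allocated group". Section 10.8 adds an analysis by treatment received.

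**The concern.** A site that follows the exclusion in section 11 would not enter an ordinary flare as an AE. A site that follows the list in section 11.4, or the inclusion of worsening illness in section 11, could enter every one. Both can point to the protocol. What enters the burning/pain/pruritus row then depends on site habit, and part of it may be the primary outcome under another name.

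The direction of the distortion is predictable. If proactive treatment reduces flares, fewer flare symptoms are available to be entered in that arm, so the row moves in its favour for a reason unrelated to drug tolerability. The proactive arm applies steroid on a schedule even without symptoms, so a true excess of local reactions there is what secondary objective 3 (safety) needs to be able to show.

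Scarring is a second overlap. It is rated by a blinded assessor as an effectiveness outcome, while AEs come from participants and site staff, who are not blinded (section 5.1, Table 4). One event can be counted twice, under two standards of assessment.

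**Working it through.** **The texts side by side**

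1. Burning sensation, pruritus and application site pain are among the known topical corticosteroid (TCS) reactions in section 2.6. Scarring is not, although section 11.1 says the known side effects taken from the product information are set out in section 11.4.
2. Section 11.3 defines a causality scale, but section 11.2 requires a causality assessment only for reportable SAEs. The scale's middle category, possible, counts as related even when concurrent disease could also explain the event. It therefore would not cleanly separate a flare from a reaction.
3. Flares are recorded every two weeks for 12 months only (section 8.1, Table 7). AEs are collected to 24 months. In months 12 to 24 there is no flare record against which an AE entry could be sorted afterwards.

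**Planning values**

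The inputs are 4 flares per year reactive, 3 proactive and dispersion k = 0.34 (Synopsis, section 10.1). As a check that they are read correctly, the plan's sample size follows from them:

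2 x (1.960 + 1.282)^2 x (1/4 + 1/3 + 2 x 0.34) / ln(3/4)^2 = 320.8, against 320 stated; and 320 / 0.80 = 400.

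**Size of the mixing**

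Let q be the share of flares that is also entered as a burning/pain/pruritus AE. Assume each flare is entered independently with probability q. The chance of at least one such entry in 12 months at flare rate m is

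P = 1 - (1 + k q m)^(-1/k).

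Let s be the proportion with a true steroid reaction, assumed independent of flares. The proportion in the row is 1 - (1 - P)(1 - s).

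For q = 10%:

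- Reactive: P = 1 - (1.136)^(-2.941) = 31.3%; with s = 5% the row shows 34.7%.
- Proactive: P = 1 - (1.102)^(-2.941) = 24.8%; with s = 10% the row shows 32.4%.
- Difference: -2.3 percentage points, against a true +5.

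The table gives the apparent difference, proactive minus reactive, in percentage points. The columns are three assumed pairs of true reaction rates (reactive v proactive).

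| q | Flare entries alone, reactive v proactive | 5% v 10% (true +5) | 5% v 15% (true +10) | 2% v 5% (true +3) |
|---|---|---|---|---|
| 0 | none | +5.0 | +10.0 | +3.0 |
| 5% | 17.6% v 13.6% | +0.5 | +4.9 | -1.3 |
| 10% | 31.3% v 24.8% | -2.3 | +1.4 | -4.0 |
| 25% | 57.7% v 48.7% | -6.0 | -3.4 | -7.3 |
| 100% | 92.0% v 87.4% | -3.8 | -3.1 | -4.2 |

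The documents give neither q nor the reaction rates. The table shows sensitivity and predicts nothing.

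**The case against.** Several points on the other side are sound.

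- **These symptoms belong on the list.** They are known reactions (section 2.6), and leaving them out would be a defect. This stands, and it argues for splitting the row rather than dropping it.
- **The sections can be read together.** On that reading a local reaction is reported and an ordinary LS symptom is not. The Synopsis speaks of adverse reactions, and Tables 3 and 7 of adverse effects of therapy. This is a reasonable reading, but section 11.4 does not state it, and the inclusion of worsening illness in section 11 points the other way.
- **Flare reports do not flow into the AE form.** Flares come from participants through two-weekly prompts, and AEs go on separate e-CRFs. This stands. Any mixing comes from sites also entering flare symptoms as AEs, at an unknown rate.
- **The e-CRF or SAP may already hold a separating field or row.** Neither is shown, so nothing here rests on its absence. The conflict in the protocol text remains.
- **Limiting treatment safety to non-flare events would bias the comparison.** Table 6 has the reactive arm apply TCS only during flares, so its application reactions arise during flares by design. This stands and shapes the fix.

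A reader might infer that the safety table will count efficacy as safety and hide steroid harm: 92% v 87% with an event, 25% fewer events on proactive, or a steroid excess of up to 1 event per person-year cancelled. The documents do not support that. Those figures require every flare to be entered as an AE. Thinning, striae, telangiectasia, infection and Cushing's syndrome are also listed separately and do not overlap with the flare symptoms.

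**Conclusion.** The conflict between sections 11 and 11.4 is in the text and should be resolved. As written, the burning/pain/pruritus row and any pooled AE total can mix flares with drug reactions, and the blinded scarring outcome can reappear as an unblinded AE.

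If proactive treatment works at the planning values, entry of as few as 5% of flares nearly removes an assumed 5-point excess of local reactions, and 10% reverses its sign. With a 10-point true excess, 10% leaves +1.4 and 25% gives -3.4. These results rest on assumed reaction rates, an assumed equal share of flares entered in each arm, and independence of flares and reactions.

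The effect is confined to symptomatic local reactions and pooled totals. Atrophy-type harms, the primary analysis, the blinded scarring analysis and the sample size are untouched.

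**What to change.** 1. Reconcile section 11 with section 11.4, stating when an LS symptom is to be entered as a targeted AE.
2. Keep collecting burning, pain and pruritus. At entry, record two items: whether the symptom occurred during an LS flare, and whether it is judged related to TCS application. Capture both up to 24 months.
3. Show the flare and non-flare strata by arm side by side. Do not restrict treatment safety to the non-flare stratum.
4. Tabulate atrophy-type harms separately from the symptoms that overlap with flares.
5. Base the between-arm comparison of scarring progression on the blinded 12- and 24-month assessments. Keep site-reported scarring, including that seen at the other visits of children and adolescents, for safety monitoring, and leave it out of pooled AE totals.

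The cost is a short addition to the AE e-CRF, a wording change in sections 11 and 11.4, and a split row in the safety table. Sample size and alpha do not change. The downside is that timing and attribution are judged by unblinded site staff, which is a further reason to show both strata.
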